2.6.6 Supplementary analyses

Not applicable.

2.7 Safety analyses

Refer to [Section 2.5](#) for details.

2.8 Pharmacokinetic endpoints

Pharmacokinetic parameters are not evaluated in this extension study.

2.9 PD and PK/PD analyses

Not applicable.

2.10 Patient-reported outcomes

Borg score

For the Borg score component, the participant will answer questions on a scale of one to ten to determine the participant's shortness of breath during the 6MWT. Larger score indicates higher breathing difficulty.

[figure not shown]
The Borg score and change from baseline will be summarized by visit and treatment group assigned in the parent study on the PD analysis set.

emPHasis-10 and PAH-SYMPACT

Refer to [Section 2.6.1.2](#) for details.

2.11 CCI

CCI

- CCI

2.12 CCI

CCI

2.13 Other Exploratory analyses

CCI

2.14 Interim analysis

Not applicable.

3 Sample size calculation

Not applicable.

4 Change to protocol specified analyses

Not applicable.

5 Appendix

5.1 Imputation rules

5.1.1 Study drug

No imputation of missing/partial start or end study drug date. If missing, the time of study end date will be imputed to 00:00:00.

5.1.2 AE date imputation

Rules for imputing the AE end date:

- If the AE end date month is missing, then the imputed end date should be set to the earliest of the study end date, 31DECYYYY or date of death.
- If the AE end date day is missing, then the imputed end date should be set to the earliest of the study end date, last day of the month or date of death.
- If AE year is missing or AE is ongoing, then the end date will not be imputed.

Rules for imputing the AE start date:

1. If imputing end dates, then this should be done prior to calculating imputed start dates.

Before imputing AE start date, find the AE start reference date.

- If the (imputed) AE end date is complete and the (imputed) AE end date < treatment start date, then AE start reference date = min(informed consent date, earliest visit date).
- Otherwise, AE start reference date = treatment start date.

Impute AE start date:

- If the AE start date year value is missing, then the date uncertainty is too high to impute a rational date. Therefore, if the AE year value is missing, then the imputed AE start date is set to NULL.
- If the AE start date year value is less than the treatment start date year value, then the AE started before treatment. Therefore:
 - If AE month is missing, then the imputed AE start date is set to the mid-year point (01JulYYYY).
 - Otherwise, if AE month is not missing, then the imputed AE start date is set to the mid-month point (15MONYYYY).
- If the AE start date year value is greater than the treatment start date year value, then the AE started after treatment. Therefore:
 - If the AE month is missing, then the imputed AE start date is set to the year start point (01JanYYYY).
 - Otherwise, if the AE month is not missing, then the imputed AE start date is set to the later of month start point (01MONYYYY) or AE start reference date + 1 day.
- If the AE start date year value is equal to the treatment start date year value:
 - If the AE month is missing, then the imputed AE start date is set to the AE reference start date + 1 day.
 - If the AE month is less than the treatment start month, then the imputed AE start date is set to the mid-month point (15MONYYYY).
 - Otherwise, if the AE month is equal to the treatment start date month or greater than the treatment start date month, then the imputed AE start date is set to the later of (month start point (01MONYYYY), AE start reference date + 1 day).

If complete (imputed) AE end date is available and the imputed AE start date is greater than the (imputed) AE end date, then imputed AE start date should be set to the (imputed) AE end date.

5.1.3 Concomitant medication date imputation

Rules for imputing the CM end date (including on-going records):

- a) If imputing end dates, this should be done prior to calculating imputed start dates.
- b) When the medication is ongoing at the end of the study, no numeric end date is derived.
- c) If the end date is completely missing no numeric end date is derived.
1. If CM end day is missing and CM month/year are non-missing, then impute CM date as the minimum of study end date and the last day of the month.
2. If CM end day/month are missing and CM year is non-missing, then impute CM date as the minimum of study end date and the end of the year (31DECYYYY).
3. If imputed CM end date is less than the complete CM start date, use the complete CM start date as the imputed CM end date.

Rules for imputing the CM start date:

- If imputing end dates, then this should be done prior to calculating imputed start dates.
- If the CM start date year value is missing, then the imputed CM start date is set to one day prior to *Treatment start date (TR01SDT)*.
- If the CM start date year value is less than the *Treatment start date (TR01SDT)* year value, then the CM started before treatment. Therefore;
- If the CM month is missing, then the imputed CM start date is set to the mid-year point (01JulYYYY).
- Else if the CM month is not missing, then the imputed CM start date is set to the mid-month point (15MONYYYY).
- If the CM start date year value is greater than the *Treatment start date (TR01SDT)* year value, the CM started after treatment. Therefore;
 - If the CM month is missing, then the imputed CM start date is set to the year start point (01JanYYYY).
 - Else if the CM month is not missing, then the imputed CM start date is set to the month start point (01MONYYYY).
- If the CM start date year value is equal to the *Treatment start date (TR01SDT)* year value;
 - And the CM month is missing or the CM month is equal to the *Treatment start date (TR01SDT)* month, then the imputed CM start date is set to one day prior *Treatment start date (TR01SDT)*.
 - Else if the CM month is less than the *Treatment start date (TR01SDT)* month, then the imputed CM start date is set to the mid-month point (15MONYYYY).
 - Else if the CM month is greater than the *Treatment start date (TR01SDT)* month, then the imputed CM start date is set to the month start point (01MONYYYY).

If complete (imputed) CM end date is available and the imputed CM start date is greater than the complete (imputed) CM end date, then imputed CM start date should be set to the complete (imputed) CM end date.

If there is no end date and ongoing check is not ticked, the CM will be considered as ongoing and included in the summary table.

5.2 AEs coding/grading

The MedDRA version which will be available at the time of database lock, will be used for the coding purpose of the adverse events.

5.3 Laboratory parameters derivations

The following table shows the direction of interest when analyzing worst case values in form of maximum and/or minimum post-baseline values. If the direction of interest is given as "High" the maximum value will be calculated and used as worst value, if the direction is given as "Low" the minimum value will be taken, and if it is given as "Low and high", both the minimum value and the maximum value will be calculated and presented in summary tables.

Table 5-1 Directions of interest for worst case value for laboratory parameters

Laboratory Parameter	Direction of interest for worst case value
A. Hematology	
Hemoglobin	Low
Hematocrit	Low
Erythrocytes	Low
WBC	Low and high
Basophils	High
Eosinophils	High
Lymphocytes	Low and high
Monocytes	High
Neutrophils	Low and high
Platelets	Low and high

B. Chemistry	
Albumin	Low
Alkaline Phosphatase	High
ALT/SGPT	High
AST/SGOT	High
Bilirubin Total	High
Blood Urea Nitrogen (BUN)	High
Creatinine	High
Gamma GT	High

Potassium	Low and high
Magnesium	Low and high
Calcium	Low and high
LDH	High
Phosphorus	Low and high
Sodium	Low and high
CRP	High
Fibrinogen	High
HbA1c	Low and high

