2.3 Benefit/Risk assessment

Potential risks are based on the mechanism of action, the nonclinical toxicology data, and the safety data from the FIH study.

LTP001 is the first SMURF1 inhibitor to be developed. Based on current understanding of SMURF1 biology, there are no concerns directly related to this mechanism of action; and, because LTP001 is first-in-class, there are no previously identified clinical safety risks (i.e., no known class effects).

Preclinical data

CCI

CCI

Clinical data

Single doses of LTP001 CCI mg, CCI mg, CCI mg, CCI mg, CCI mg and CCI mg were well tolerated and did not show safety signals for LTP001 in the first in human study.

Multiple doses of LTP001 CCI mg, CCI mg, CCI mg, CCI mg and CCI mg once daily and CCI mg bid were well tolerated. CCI

CCI , clinical laboratory assessments, ECGs, and vital signs did not show significant abnormalities. CCI

The risk to participants in this trial will be minimized by adherence to the eligibility criteria, close clinical monitoring, regular safety data reviews, and pre-specified rules for automatically stopping the study should unanticipated safety issues suddenly arise.

No reproductive toxicology studies have been performed for LTP001. Women of child-bearing potential will be only enrolled if they use highly effective contraception methods.

Additional details about potential risks of LTP001 can be found in the Investigator's Brochure.

Procedural risks

Cardiac catheterization is a safe procedure when performed by an experienced medical team. However, there may be some possible risks such as bleeding, infection, and blood clots. A heart attack or a stroke can happen in very rare situations. Right heart catheterization (RHC) is regularly employed to monitor the course of PAH. RHC may be performed without radiation but for optimal placement of the catheter, the investigator can employ x-ray to double-check the positioning of the catheter when measurements are made. RHC does not employ contrast media. RHC is required to calculate PVR. PVR was the primary efficacy assessment of the

parent study, CLTP001A12201, and is performed at Week 26 in the current study, which allows the assessment of the 1-year effect of LTP001 of those participants who received LTP001 already in the parent study, and the 6-month effect on PVR of those who received placebo in the parent study. This data is considered very important to assess the long-term effect of LTP001 on PVR in patients with PAH.

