The safety and efficacy of LTP001 will be checked at the following visits: Weeks 5, 13, 26, 39 and 52, as specified in the Assessment Schedule. Safety and tolerability assessments will take place at each visit. RHC will be performed at week 26 and 6MWT and echocardiography will be assessed at Weeks 26 and 52. PAH-SYMPACT and emPHasis-10 will be collected for 7 day intervals with the seventh day of collection occurring within the allotted visit window for all Treatment visits (Weeks 5, 13, 26, 39 and 52). Participants will have safety follow-up phone calls at Weeks 9 and 17, and may be invited for safety assessment at site if deemed necessary. The PI may exercise their discretion in which safety assessments are required at these optional safety follow-up visits. Following the end of treatment period, participants will have one safety follow-up phone call approximately 30 days after the end of treatment visit at Week 52. The duration of the extension study is currently restricted to 52 weeks, but the study may be prolonged (via an amendment to the protocol) if the LTP001 development program in PAH continues and the benefit/risk assessment remains favorable for the patient population studied. The safety and efficacy profile of LTP001 that is observed in this extension study as well as the parent study, CLTP001A12201, will determine continuation of the extension study.

Please refer to [Figure 1-1](#) for study design figure.

Figure 1-1 Study Schema

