Categorical Analysis of QTcF (Fridericia's formula) interval data based on the number of participants meeting or exceeding predefined limits in terms of absolute QT or QTc intervals or changes from baseline will be presented. The number and percentage of participants with clinical notable QTcF will be summarized by visit. A listing of these participants will be provided. The clinical notable criteria for QTcF (Fridericia's formula) are indicated in [Table 2-2](#).

Table 2-2 Clinical notable criteria for QTcF (Fridericia's formula)

ECG parameter (unit)	Clinically notable range
Notable value considering newly occurring or worsening cases	
QTcF (msec)	> 500
QTcF (msec)	> 480 if normal at baseline
QTcF (msec)	> 450
Notable change from baseline	
QTcF (msec)	> 60
QTcF (msec)	> 30

Laboratory data

All laboratory data will be listed by participant and visit/time and if normal ranges are available, abnormalities will be flagged. A separate listing is provided presenting all parameters in a subject with any abnormal values. Descriptive statistics (N, mean, SD, minimum, median, and maximum) summarizing continuous laboratory results of clinical chemistry, hematology, urinalysis, and changes from baseline by visit/time will be provided. Graphical presentations (e.g., boxplots) will be provided by visit/time.

Shift tables using the low/normal/high/ (low and high) classification will be used to compare baseline to the worst on-treatment value.

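### SAP Table 5-1 takes only the minimum as the worst value for hemoglobin, hematocrit and erythrocytes, so the laboratory shift table cannot properly count participants who move to high

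*SAP*

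**What the plan says.** Three parts of the plan combine.

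- **Directions.** SAP 5.3, Table 5-1, lists "Hemoglobin Low", "Hematocrit Low" and "Erythrocytes Low". In the same hematology block, WBC, lymphocytes, neutrophils and platelets are *Low and high*. So are six entries in the chemistry block (potassium, magnesium, calcium, phosphorus, sodium, HbA1c).
- **Rule.** The text above the table says that for direction *Low* "the minimum value will be taken, and if it is given as" *Low and high*, then "both the minimum value and the maximum value will be calculated and presented in summary tables".
- **Use.** SAP 2.5.1, under laboratory data: "Shift tables using the low/normal/high/ (low and high) classification will be used to compare baseline to the worst on-treatment value". Laboratory measurements are part of the primary safety endpoint.

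SAP 2.5.1 also specifies other laboratory outputs:

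- a listing by participant and visit with abnormal values flagged;
- a separate listing of all parameters for participants with any abnormal value;
- by-visit N, mean, SD, minimum, median and maximum;
- changes from baseline;
- boxplots.

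**The concern.** The shift table has a high category and a combined low-and-high category. For the three red-cell tests, however, only the minimum feeds it. A minimum lies above the upper limit of normal only when all values do, so an isolated or intermittent rise leaves no trace in that table.

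At stake is a participant-level count. The shift table is the only numerical laboratory summary in the SAP that classifies participants by where their values fall against the normal range. By-visit maxima show the most extreme value at each visit, not how many participants crossed the limit. Listings hold the information but give no rate.

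The protocol describes LTP001 as the first drug of its class and states that "there are no previously identified clinical safety risks (i.e., no known class effects". The visible text therefore gives no prior expectation that only decreases in these tests are of interest.

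**Working it through.** The plan states no figure for this point (sample size is given as not applicable), so there is nothing to reproduce. The check has a logical part, which needs no assumptions, and an illustrative part, which does.

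**Inputs from the documents**
- Direction *Low*, minimum taken, for three tests: SAP 5.3 and Table 5-1.
- Five scheduled on-treatment visits: "The safety and efficacy of LTP001 will be checked at the following visits: Weeks 5, 13, 26, 39 and 52" (SAP 1.1). Optional safety assessments at Weeks 9 and 17 could make seven.
- About 40 participants: Protocol section 5.

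**Part 1: what the rule does**

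Classify each visit as low, normal or high, enumerate all patterns with at least one high value, and apply the minimum.

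| Visits | Patterns | Any high | Shown low | Shown normal | Shown high |
|---|---|---|---|---|---|
| 5 | normal/high only | 2^5 − 1 = 31 | – | 30 | 1 |
| 7 | normal/high only | 2^7 − 1 = 127 | – | 126 | 1 |
| 5 | low values allowed | 3^5 − 2^5 = 211 | 180 | 30 | 1 |

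These are counts of patterns, not probabilities. In every row the only pattern shown as high is the one with all values high. A participant with both a low and a high value is shown as low. One minimum cannot fall in the low-and-high category. If the maximum is also taken, all 31, 127 and 211 patterns are captured as having a high value.

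**Part 2: hypothetical size**

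The documents give no rate of high values. Assume a chance p of a high value at each measurement, including baseline, and within-person correlation ρ, modelled as beta-binomial with a = p(1 − ρ)/ρ and b = (1 − p)(1 − ρ)/ρ.

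For p = 0.10 and ρ = 0.5, a = 0.1, b = 0.9 and a + b = 1.

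- Not high at baseline: 0.9.
- Not high at baseline or at any of five visits: 0.9 × (1.9/2) × (2.9/3) × (3.9/4) × (4.9/5) × (5.9/6) = 0.7766.
- Not high at baseline, at least one high later: 0.9 − 0.7766 = 0.1234, and 40 × 0.1234 = 4.9 participants.
- High at five given measurements: 0.1 × (1.1/2) × (2.1/3) × (3.1/4) × (4.1/5) = 0.02447.
- High at six: 0.02447 × (5.1/6) = 0.02080.
- Not high at baseline, high at all five visits (so shown as high): 0.02447 − 0.02080 = 0.00367, and 40 × 0.00367 = 0.15 participants.

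The same formulas with other correlations, p = 0.10:

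| ρ | New high value (of 40) | Shown as high (of 40) |
|---|---|---|
| 0.3 | 7.8 | 0.09 |
| 0.5 | 4.9 | 0.15 |
| 0.7 | 2.7 | 0.14 |

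If baseline is ignored, p = 0.10 and ρ = 0.5 give 40 × (1 − 0.7897) = 8.4 participants with any high value and 40 × 0.02447 = 1.0 shown as high. The difference, 8.4 − 4.9 = 3.5, is participants already high at baseline, who are not new shifts. The baseline-restricted figures are the ones to use.

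**The case against.** The strongest case on the other side is that this is a prespecified choice and not an error. Table 5-1 states directions of interest and is one-sided for many tests, such as albumin (*Low*) and creatinine and LDH (*High*). No passage requires red-cell increases to be counted. That stands: the documents do not contradict themselves here, and the point is an improvement rather than a correction.

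Three stronger readings are tempting, and the documents do not support them.

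- **That a rise could go unseen in the primary safety result.** The flagged listings, the separate abnormal-value listing, by-visit maxima, changes from baseline and boxplots would all show it. Protocol 8.4.2 requires abnormal results to be assessed against the adverse-event criteria. Protocol 8.6.1 makes clinically significant values adverse events, and SAP 2.5.1 counts participants with those. With about 40 participants, the remaining excursions could be counted by hand from the listing. Only the shift-table count is lost.
- **That no justification exists for looking at decreases only.** Preclinical and some clinical text in Protocol 2.3 is redacted, as is part of Protocol 8.4.4. One can say only that no reason is visible. The visible clinical text reports no significant laboratory abnormalities, so nothing visible points to a rise on LTP001.
- **That diuretic adjustment or falling oxygen saturation makes such rises likely here.** Neither document makes that link, and the point does not need it.

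It is also fair to object that the rates in the illustration are assumed. They are. The logical result in Part 1 does not depend on them.

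**Conclusion.** The point holds as a minor one. For hemoglobin, hematocrit and erythrocytes, the shift table shows a participant as high only when every on-treatment value is high, and its low-and-high category is unusable. This follows from SAP 5.3 and 2.5.1 without assumptions.

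The size is hypothetical. With 40 participants, five visits and a 10% chance of a high value per measurement, about 4.9 participants would have a new high value against about 0.15 shown as high at correlation 0.5. Across correlations 0.3 to 0.7 the figures are about 7.8 to 2.7 against 0.09 to 0.14. Extra assessments at Weeks 9 and 17 would make the all-high condition harder to meet.

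The data are not lost and other outputs show them. The gap is one participant count in a descriptive safety table.

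**What to change.** In SAP Table 5-1, change the direction for hemoglobin, hematocrit and erythrocytes from *Low* to *Low and high*. Both the minimum and the maximum then enter the shift tables, as already planned for WBC, lymphocytes, neutrophils and platelets, and the low-and-high category becomes usable for these tests.

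The cost is three table entries and a few extra rows of output. No new data are needed and nothing changes for participants. If the one-sided choice was deliberate, a sentence in SAP 5.3 giving the reason would be the alternative, but the count would still be missing.

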5.4 Statistical models

Not applicable.

5.5 Rule of exclusion criteria of analysis sets

Refer to [Table 2-1](#) for details.

6 Reference

ICH E9(R1) Harmonized Guideline: addendum on estimands and sensitivity analysis in clinical trials to the guideline on statistical principles for clinical trials. Final version on 20 November 2019.
